#### **Secondary endpoints**

Survival at Days 42, 90, 180 and 365

The survival rates will be compared with the same methods as described above for the analysis of composite event rate.

*Incidence of liver related death at Days* 42, 90, 180 and 365.

† ACLF: Acute on Chronic Liver Failure; **Grade 1:** a) Single kidney failure, b) Single liver, coagulation circulatory or respiratory failure + creatinine 1.5-1.9 mg/dL and/or HE I-II, c) Single cerebral failure (HE III-IV) + creatinine 1.5-1.9 mg/dL; **Grade 2:** 2 organ failures; **Grade 3:** 3 or more organ failure score.

The association of study arms with rebleeding hazard function will be tested using univariate and multivariate Cox models. The cumulative risk of rebleeding during follow-up in each arm will be estimated by calculating the cumulative incidence function (CIF) rebleeding at 12 months. In this approach, death for other causes during follow-up will be considered as a competing event.

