#### **Secondary objectives:**

Demonstrate the efficacy of an "early-TIPS" strategy to reduce:

- 1/ All-cause mortality rate at Days 42 and 365.
- 2/ Liver related mortality rate at Days 42, 90, 180 and 365.
- 3/ Rebleeding rate at Days 42, 90, 180 and 365.
- 4/ Cumulative incidence of complications of cirrhosis at Day 365.
- 5/ Transfusion requirements at Days 42 and 365.

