## **6.2 Analysis Methods**

Analyses of all endpoints will be performed on the mITT as well as the per protocol population unless specified.

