#### *Incidence of rebleeding during follow-up*

The association of study arms with rebleeding hazard function will be tested using univariate and multivariate Cox models. The cumulative risk of rebleeding during follow-up in each arm will be estimated by calculating the cumulative incidence function (CIF) rebleeding at 12 months. In this approach, death free of rebleeding during follow-up will be considered as a competing event.

Incidence of the other complications of liver cirrhosis during follow-up

The association of treatment group with the hazard function of other complications will be tested using univariate and multivariate Cox models. The cumulative risk of other complications during follow-up in each arm will be estimated by calculating the CIF at 12 months. In this approach, death free of complications during follow-up will be considered as a competing event.

Cumulative number of packed red blood cells required by each treatment arms.

Variation of MELD score between inclusion and 6 months in each arm

Number of days that patients spend in hospital during follow-up

Comparison between strategy groups will be performed with Student's t-test or the Mann-Whitney test, as appropriate.

Frequency of TIPS technical failure and TIPS complications: thrombosis, heart failure, infection and encephalopathy. Frequency of technical failure of GO and complications of GO: migration of glue, infection of the site of injection, significant bleeding during the procedure (hospital stay, blood transfusion, 3 g drop in hemoglobin).

This analysis will be performed on the safety population.

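### SAP 6.2: the method given under the liver-related death heading names rebleeding as its event, so as written secondary endpoint 2 has no analysis

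*SAP*

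**What the plan says.** The secondary objectives in SAP Section 2 include, as number 2, a reduction in "Liver related mortality rate at Days 42, 90, 180 and 365" and, as number 3, a reduction in "Rebleeding rate at Days 42, 90, 180 and 365". Section 6.1 lists both as separate secondary endpoints at the same four days and defines liver-related death through a table of ICD-10 cause categories.

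Section 6.2 then gives each endpoint its method. Under the heading for liver-related death, the first sentence reads: "The association of study arms with rebleeding hazard function will be tested using univariate and multivariate Cox models". The second and third sentences turn to cumulative risk and contain the words "cumulative incidence function (CIF) rebleeding at 12 months. In this approach, death for other causes during follow-up", the last of these being the competing event.

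The next heading is rebleeding during follow-up. Its first two sentences are the same, and its third says that "death free of rebleeding during follow-up will be considered as a competing event". The paragraph after that, on other complications of cirrhosis, has the same structure with its own event: "The association of treatment group with the hazard function of other complications will be tested using univariate and multivariate Cox models", and "death free of complications during follow-up will be considered as a competing event".

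The opening of section 6.2 applies the methods to two populations: "Analyses of all endpoints will be performed on the mITT as well as the per protocol population unless specified".

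**The concern.** The heading and the method beneath it describe different events. Liver-related death is a cause-specific death, while rebleeding is a non-fatal clinical event with its own definition in section 6.1. A Cox model and a CIF for one say nothing about the other.

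An analysis programmed from section 6.2 as written would put a second rebleeding analysis under the liver-related death heading and leave objective 2 without a result. Someone checking the report against the SAP would find no prespecified analysis matching endpoint 2. The same sentences govern both the modified intention-to-treat and the per-protocol analysis, so the slip would appear in both.

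**Working it through.** No power or sample size figure is involved, so the check is a comparison of text. The inputs are the three parallel method paragraphs in SAP 6.2, the secondary objectives in Section 2, and the endpoint list and definitions in 6.1.

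**1. Word-by-word comparison of the liver-related death and rebleeding paragraphs**

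- Sentence 1 (Cox models): 18 words in each, identical; rebleeding named once.
- Sentence 2 (CIF): 24 words in each, identical; rebleeding named twice.
- Sentence 3 (competing event): 58 − 18 − 24 = 16 words in each; three words differ and 13 are the same.
- Total: 58 words in each paragraph, of which 18 + 24 + 13 = 55 are identical. Rebleeding is named as the event 1 + 2 = 3 times under the liver-related death heading. The word liver does not occur in that method paragraph.

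**2. The three paragraphs side by side**

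| Heading in 6.2 | Event in the Cox model | Event in the CIF | Competing event |
|---|---|---|---|
| Liver-related death | Rebleeding | Rebleeding | Death from other causes |
| Rebleeding | Rebleeding | Rebleeding | Death without rebleeding |
| Other complications | Other complications | Other complications | Death without complications |

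In the second and third rows the heading, event and competing event agree. In the first row only the competing event was adapted. This is the pattern of a copied paragraph whose editing was not finished.

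**3. Could the PDF conversion have caused it?** A table footnote on acute-on-chronic liver failure falls between the heading and the paragraph, which is a matter of page layout. The paragraph is not a duplicate of the next one, because its third sentence differs. It also stands before the rebleeding heading.

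**4. Is a method given elsewhere?** The sentence in 6.2 that carries the primary endpoint's methods over to a secondary endpoint covers survival only. The opening sentence of 6.2 sets populations and no method. No other section names a method for liver-related death.

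**5. Count of analyses on the literal reading.** Rebleeding: two. Liver-related death: none. Endpoints affected: one of the ten numbered secondary endpoints.

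**6. Reporting days.** The CIF sentences for liver-related death and for rebleeding say 12 months, whereas objectives 2 and 3 and endpoints 2 and 3 list Days 42, 90, 180 and 365. A CIF estimated to 12 months already contains the values at the earlier days, so this affects only what is reported.

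**The case against.** The strongest reply is that nobody would be misled. The heading names liver-related death, the objectives and endpoint list repeat it, section 6.1 defines it, and the competing event is already given. A programmer would have to produce a rebleeding table under a heading that says otherwise, directly before a section devoted to rebleeding. On this view the point is editorial.

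Most of that stands. There is one coherent reading, the slip opens no room for a data-driven choice, and no result changes if that reading is followed. This limits the weight of the point. It does not make the text right: an operative analysis rule for a named secondary objective specifies the wrong event, and the SAP is the reference against which programs and reports are checked.

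Two narrower objections also deserve weight. First, death from other causes does not say other than what. Next to sentences about rebleeding, it could be taken to mean causes other than rebleeding, so the phrase alone does not prove the intent; the heading settles it. Second, the reporting days for liver-related death already stand in its 6.2 heading, and those for rebleeding in Section 2 and 6.1. Nothing is undefined, and aligning the days is a convenience.

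**Conclusion.** The concern holds. Under the liver-related death heading, section 6.2 specifies an analysis of rebleeding, named three times in 42 words carried over unchanged from the neighbouring paragraph. As written, secondary endpoint 2 has no analysis and rebleeding has two. The text should be corrected, but the weight is modest: one of ten numbered secondary endpoints is affected, plus the reporting days of endpoint 3. The primary endpoint, all-cause survival and the sample size are untouched.

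The statement that endpoint 2 has no analysis rests on the literal reading and on the SAP alone, since the protocol is not at hand. On the inferable reading, with liver-related death as the event and death from other causes as the competing event, the numerical consequence is nil.

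**What to change.** In SAP 6.2, in the paragraph under the liver-related death heading:

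- Replace rebleeding by liver-related death in all three places: once in the Cox sentence and twice in the CIF sentence.
- Keep death from other causes as the competing event, and leave the model types as they are.

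Keep the following paragraph as the only analysis of rebleeding. As an optional alignment, change the 12-month phrase to Days 42, 90, 180 and 365 in the liver-related death and rebleeding paragraphs. The complications paragraph can stay at 12 months, which matches endpoint 5.

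The cost is three word replacements, two time-point phrases if the alignment is made, and an entry in the SAP's Revision Control table. No new data, definition or method is needed, and there is no statistical downside.

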#### *Incidence of rebleeding during follow-up*

The association of study arms with rebleeding hazard function will be tested using univariate and multivariate Cox models. The cumulative risk of rebleeding during follow-up in each arm will be estimated by calculating the cumulative incidence function (CIF) rebleeding at 12 months. In this approach, death free of rebleeding during follow-up will be considered as a competing event.

Incidence of the other complications of liver cirrhosis during follow-up

The association of treatment group with the hazard function of other complications will be tested using univariate and multivariate Cox models. The cumulative risk of other complications during follow-up in each arm will be estimated by calculating the CIF at 12 months. In this approach, death free of complications during follow-up will be considered as a competing event.

Cumulative number of packed red blood cells required by each treatment arms.

Variation of MELD score between inclusion and 6 months in each arm

Number of days that patients spend in hospital during follow-up

Comparison between strategy groups will be performed with Student's t-test or the Mann-Whitney test, as appropriate.

Frequency of TIPS technical failure and TIPS complications: thrombosis, heart failure, infection and encephalopathy. Frequency of technical failure of GO and complications of GO: migration of glue, infection of the site of injection, significant bleeding during the procedure (hospital stay, blood transfusion, 3 g drop in hemoglobin).

This analysis will be performed on the safety population.

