#### **Secondary endpoints**

- 1- Survival at Days 42, 90, 180 and 365.
- 2- Incidence of liver related death at Days 42, 90, 180 and 365.
- 3- Incidence of significant rebleeding at Days 42, 90, 180 and 365.
- 4- Cumulative number of packed red blood cells required by each treatment arms.
- 5- Incidence of complications of cirrhosis during the 12-month follow-up.
- any of the complication below
- bacterial infections,
- jaundice,
- ascites.
- spontaneous bacterial peritonitis,
- hepatic encephalopathy,
- hepatorenal syndrome,
- further decompensation.
- 6- Frequency of:
- TIPS technical failure and TIPS complications: thrombosis, heart failure, infection and encephalopathy.

- Technical failure of GO and complications of GO: migration of glue, infection of the site of injection, significant bleeding during the procedure (hospital stay, blood transfusion, 3 g drop in hemoglobin).
- 7- Number of patients lost to follow up at Day 365 in each group
- 8- Change of MELD score between inclusion and Day 180 in each group.
- 9- Number of days spent in hospital in each group during the 12-months follow-up.
- 10- Number of bacterial infections and localizations.

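### Rebleeding and liver-related death are defined at Days 42, 90, 180 and 365, but the methods give rebleeding a 12-month estimate only, liver death no analysis as printed, and no endpoint a between-arm comparison at the earlier days

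*SAP*

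**What the plan says.** **Objectives (section 2, Secondary objectives).** The stated aim is to demonstrate that early TIPS reduces three outcomes at named days: "All-cause mortality rate at Days 42 and 365"; "Liver related mortality rate at Days 42, 90, 180 and 365"; "Rebleeding rate at Days 42, 90, 180 and 365".

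**Endpoints (section 6.1, Secondary endpoints).** These are "Survival at Days 42, 90, 180 and 365", "Incidence of liver related death at Days 42, 90, 180 and 365" and "Incidence of significant rebleeding at Days 42, 90, 180 and 365". All three carry four days, whereas the mortality objective carries two.

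**Methods (section 6.2).**
- Survival: the heading repeats the four days, and the text reads "The survival rates will be compared with the same methods as described above for the analysis of composite event rate". Those methods are Kaplan-Meier over 12 months, a log-rank test, and a Cox model with a Schoenfeld-residual check and a time-dependent term if proportional hazards fail.
- Liver-related death: the heading repeats the four days. The text beneath it refers to the rebleeding hazard and the 12-month rebleeding CIF. Only the competing event, death from other causes, fits liver-related death.
- Rebleeding: the heading no longer names any day. The test is a Cox model with no stated horizon, and the estimate is: "The cumulative risk of rebleeding during follow-up in each arm will be estimated by calculating the cumulative incidence function (CIF) rebleeding at 12 months". Death free of rebleeding is the competing event.

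Section 4.1 promises 95% confidence intervals for secondary effect estimates.

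**The concern.** Objectives and endpoints that name a day call for an estimate at that day. For rebleeding, the methods supply one only at 12 months. For liver-related death, the printed text supplies none at any day. For survival, the curve contains the values, but nothing says how the arms are to be compared at Day 42, 90 or 180. The confidence intervals promised in section 4.1 have no day-specific effect to attach to.

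This matters because the effect may change over the year. Section 3.1 places TIPS once, before Day 4, and spreads glue sessions over the year to Day 365. A contrast over all follow-up averages across those periods. If the early objectives have no planned analysis, they will either go unanswered or be answered by a method chosen after the data are seen.

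**Working it through.** **Step 1. Set the sections side by side.**

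| Outcome | Objective days | Endpoint days | Estimate in 6.2 | Between-arm comparison in 6.2 |
|---|---|---|---|---|
| All-cause death | 42, 365 | 42, 90, 180, 365 | Kaplan-Meier over 12 months | Log-rank and Cox, no day stated |
| Liver-related death | 42, 90, 180, 365 | 42, 90, 180, 365 | As printed, a rebleeding CIF at 12 months | As printed, a Cox model for rebleeding |
| Rebleeding | 42, 90, 180, 365 | 42, 90, 180, 365 | CIF at 12 months | Cox, no day stated |

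No section states a difference, an interval, a truncated test or a fixed-day test at Day 42, 90 or 180.

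**Step 2. How much information lies early?** The SAP gives no day-specific rates, so there is no figure of its own to reproduce on this point. As an illustration, take the composite rates in section 3.3 (15% TIPS, 40% glue at 12 months, 52 per arm) and assume constant hazards and no dropout. The risk at day d is 1 − (1 − p)^(d/365), and expected events are 52 × (sum of the two risks).

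| Day | TIPS | Glue | Expected events | Power, two-sided 0.05 |
|---|---|---|---|---|
| 42 | 1.9% | 5.7% | 3.9 | 0.18 |
| 90 | 3.9% | 11.8% | 8.2 | 0.32 |
| 180 | 7.7% | 22.3% | 15.6 | 0.55 |
| 365 | 15% | 40% | 28.6 | 0.82 |

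For Day 42: 1 − 0.85^(42/365) = 0.0185; 1 − 0.60^(42/365) = 0.0571; 52 × 0.0756 = 3.9. An approximate 95% interval for the difference is 0.0386 ± 1.96 × √[(0.0185 × 0.9815 + 0.0571 × 0.9429)/52] = 0.0386 ± 0.073, roughly −3 to 11 percentage points. Normal intervals are crude with so few events, but the width is clear. Rebleeding or liver death alone cannot have more events than a composite that contains it.

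**Step 3. Does a whole-follow-up test inform Day 42?** Illustration only: piecewise-constant hazards with a change at Day 42, 12-month risks held at 15% and 40%, 52 per arm, no dropout, two-sided 0.05, 4,000 simulated trials per row.

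| Day 42 risk, TIPS vs glue | Log-rank over 12 months rejects | Log-rank truncated at Day 42 rejects |
|---|---|---|
| 5% vs 5% | 80% | 5% |
| 10% vs 10% | 79% | 5% |
| 1.9% vs 5.7% (proportional) | 84% | 15% |
| 5% vs 20% | 85% | 67% |

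The 12-month test rejects in 79% to 85% of trials whether the Day 42 difference is zero or 15 points, so it does not distinguish these cases. These rejections are not false positives: a 25-point difference at one year exists in every row. They simply do not answer a Day 42 question.

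**The case against.** Four points can be made for the plan.

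- *The curves hold the values.* A Kaplan-Meier or CIF curve to 12 months contains Days 42, 90 and 180. This stands for survival and, in principle, for rebleeding. The gap is in what is specified and compared, not in what could be estimated.
- *The survival text can be read as covering each day.* The heading names the four days and the text says the rates will be compared, which may mean at each horizon. This reading is open, so for survival the matter is ambiguity, not error. A reader might infer that mortality has only a 12-month CIF. It does not: survival inherits Kaplan-Meier, log-rank and Cox.
- *The plan provides for non-proportional hazards.* This is true for survival. The provision is not stated for rebleeding or liver death, and a time-dependent term does not by itself give a risk difference at Day 42.
- *A Cox hazard ratio alongside a CIF with death competing is a standard pairing.* This stands. The pairing is sound as a summary of all follow-up; it does not deliver the day-specific endpoints.

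A reader might also infer that the 12-month hazard ratio will be reported as the Day 42 result. The SAP nowhere says so, and that would be a prediction about reporting.

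Finally, adding contrasts has a price: three endpoints at four days make 12 differences, and the early ones will be imprecise.

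**Conclusion.** The point holds in a limited form. For rebleeding, the objectives and endpoints name four days and the methods deliver an estimate at one. For liver-related death, the paragraph appears to be carried over from rebleeding with only the competing event changed; read literally, no liver-death analysis is stated. For all-cause survival, day-specific values are available from the curve, but no comparison at Day 42, 90 or 180 is set out, and the objectives (two days) disagree with the endpoints (four).

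These conclusions rest on the text alone. The event counts and rejection rates are illustrations that borrow the composite rates and assume hazard shapes the SAP does not give. They show why a 12-month contrast cannot stand in for an early one; they do not estimate what this trial will find. The primary analysis is untouched. The correction should be made before the final analysis because three secondary efficacy objectives currently have no matching early comparison.

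**What to change.** In the secondary-endpoint part of section 6.2:

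1. For all-cause death, state the Kaplan-Meier estimate per arm at Days 42, 90, 180 and 365, with the between-arm difference and 95% CI at each day.
2. For liver-related death (other death competing) and rebleeding (death free of rebleeding competing), state the CIF per arm at the same four days, again with the difference and 95% CI.
3. Rewrite the liver-death paragraph so that the hazard and the CIF refer to liver-related death.
4. Keep the Cox hazard ratio, labelled as a summary over the whole follow-up.
5. Bring the mortality days in the secondary objectives into line with the four days in section 6.1.
6. Say that the day-specific contrasts are estimates with intervals, not separate confirmatory tests, since section 4.1 otherwise applies the 0.05 threshold to every test.

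The cost is SAP wording and a few lines of code, with no new data. The downside is wide intervals at the early days, which should be acknowledged in the text.

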## 3.3 Sample size

The sample size is calculated with a projected rate of composite event of failure at 12 months of 15% in the group "TIPS" [estimated from Garcia Pagan, New Engl J Med 2010] versus 40% in the group « glue» [estimated from Hou, Gastrointest Endosc 2009].

A number of 52 patients in each group will achieve 80% power to detect TIPS superiority using a one-sided logrank test at a 0,050 significance level, with a proportion dropping out of both groups of 10%.

Total number of scheduled patients recruited or observations collected: 104.

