## 5.2 Withdrawal/Follow-up

Criteria for stopping the study are:

- withdrawal of consent,
- liver transplantation,
- loss to follow up,
- enrollment of ineligible subjects.

Patients withdrawn from the study for withdrawal of consent, liver transplantation or loss to follow up will be censored at the date of withdrawal. Ineligible subjects will be excluded from the mITT analyses. Unless consent to analyze data is also withdrawn, all the data collected prior to withdrawal from the study will be considered for analysis.

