## **6.3 Missing Data**

In general, missing values will remain as missing, i.e., no attempt will be made to impute missing values and only observed values will be used in data analyses and presentations.

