#### Survival analysis

All patients not reaching any event at the end of follow-up or before their last assessment (for patients lost to follow-up) will be censored at the date of their last assessment visit. Patients receiving a liver transplant will be censored at the time of liver transplantation.

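### Two secondary analyses in SAP Section 6.2 need tightening: MELD change is tested without using inclusion MELD, and the red-cell total lacks the Day 42 and Day 365 windows its objective sets.

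*SAP*

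**What the plan says.** Section 6.2 (Analysis Methods, secondary endpoints) lists three quantities together: red-cell units, MELD variation from inclusion to 6 months, and days in hospital. One sentence covers all three: "Comparison between strategy groups will be performed with" Student's t-test or the Mann-Whitney test, as appropriate. No covariate is named. Section 5.3 includes MELD among the scores described at baseline.

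The secondary objectives in Section 2 include "Transfusion requirements at Days 42 and 365" among the outcomes that early TIPS is meant to reduce. The matching endpoint in Section 6.1 reads "Cumulative number of packed red blood cells required by each treatment arms" and gives no day or period. Section 6.2 repeats it, also without a window. By contrast, Section 6.1 attaches explicit days to survival, liver-related death and rebleeding.

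On incomplete follow-up, Section 5.2 says that patients withdrawn for consent withdrawal, "liver transplantation or loss to follow up will be censored at the date of withdrawal". It adds that, unless consent to analysis is also withdrawn, "all the data collected prior to withdrawal from the study will be considered for analysis". Section 6.3 states that "no attempt will be made to impute missing values and only observed values will be used in data analyses". Under its survival-analysis heading it adds: "Patients receiving a liver transplant will be censored at the time of liver transplantation".

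**The concern.** Three matters arise from that one sentence.

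- **MELD.** A change-score test ignores a baseline value that is already recorded and that predicts the Day 180 value. With 52 patients per arm, and fewer alive and measured at Day 180, unused precision is worth recovering. The comparison also applies only to patients with a Day 180 value, and the SAP does not say so.
- **Red cells.** The objective has two time points and the endpoint and analysis have none. An analyst working from Sections 6.1 and 6.2 alone would naturally take the whole of follow-up and could omit Day 42.
- **Totals cut short.** A t-test or Mann-Whitney on a total has no way to use censoring. The SAP does not say in so many words whether the partial total of a transplanted, withdrawn or lost patient goes in as it stands or is left out.

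At stake are the precision and reproducibility of secondary results. The primary endpoint is untouched.

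**Working it through.** **1. MELD: variance of the two analyses**

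The plan gives no figure here to reproduce. Let MELD have the same SD, s, at inclusion and at Day 180, with within-arm correlation r. The SAP does not give r, so 0.5 to 0.9 is an assumption.

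- Variance of a change score: 2s²(1 − r)
- Residual variance under ANCOVA on inclusion MELD: s²(1 − r²)
- Ratio, ANCOVA to change score: (1 − r²) / [2(1 − r)] = (1 + r)/2

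| r | (1 + r)/2 |
|---|---|
| 0.5 | 0.75 |
| 0.7 | 0.85 |
| 0.9 | 0.95 |

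The gain is real but modest, and small if r is high. It refers to the difference in mean change, not to the Mann-Whitney test.

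**2. MELD: who is compared**

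Inputs: 52 per arm and 10% drop-out (Section 3.3); deaths by Day 180 assumed to be 20% in one arm and 7.5% in the other. Loss by Day 180, if even over the year, is 10% × 180/365 = 4.9%.

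- 52 × 0.80 × 0.951 ≈ 40
- 52 × 0.925 × 0.951 ≈ 46

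Survivor selection can then shift the comparison even with no true effect on MELD. Assume SD 5, r = 0.5 and a normally distributed liability to death. The difference between arms in survivors' mean liability is 0.350 − 0.153 = 0.197 SD.

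- If death depends on inclusion MELD (assumed correlation 0.5), the change score shifts by 0.197 × 0.5 × 5 × (1 − 0.5) ≈ 0.25 points. ANCOVA brings this to 0.00.
- If death tracks the later MELD (assumed correlation 0.8), the change score shifts by 0.197 × 0.8 × 5 × (1 − 0.5) ≈ 0.39 points. In simulation, ANCOVA gives 0.62.

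ANCOVA therefore corrects selection acting through inclusion MELD, but not selection on later deterioration, where its shift can be somewhat larger.

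**3. Red cells: the three places side by side**

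| Place in SAP | Window |
|---|---|
| Section 2, secondary objectives | Days 42 and 365 |
| Section 6.1, endpoint | none |
| Section 6.2, analysis | none |

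Follow-up is 12 months, so an unqualified total would most likely be read as Day 365. Day 42 is the time point at risk.

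**4. Totals cut short**

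At the documented 10% drop-out, 52 × 0.10 = 5.2 patients per arm are affected. With losses even over the year and constant use, the mean observed total is 0.90 + 0.10 × 0.5 = 0.95 of the full total in each arm, so the ratio between arms is 0.95/0.95 = 1.00.

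With assumed deaths of 20% v 7.5% added (even over 90 days, constant use, loss unrelated to use), simulation gives a true ratio of 0.885, against 0.886 to 0.887 when partial totals are entered as observed and 0.878 when those patients are left out.

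Unequal loss matters more, but the rates are invented. With the same deaths and losses of 15% v 5%, a true 0.882 reads 0.839 (entered as observed) or 0.861 (left out). With no deaths, losses of 15% v 5% and high users lost preferentially, a true 1.00 reads 0.89 or 0.85. Neither rule is uniformly better.

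**The case against.** The strongest reply is that little here is an error. The change-score test is valid under randomisation, MELD and hospitalization fall under the objectives to be described rather than demonstrated (Section 2), and ANCOVA can be called a preference. That is fair on validity. ANCOVA nevertheless uses a value already collected and costs almost nothing. Its possible enlargement of the survivor shift depends on how death relates to MELD, so it calls for a caveat and does not defeat the proposal.

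On red cells, Day 42 does stand in the objectives of this same SAP, so a careful analyst would probably report it. A reader might infer that Day 42 will go unreported; the text supports only that the endpoint and analysis sections fail to carry it through.

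On partial totals, a reader might infer that the plan has no place for them and that the comparison is biased. Sections 5.2 and 6.3 together most naturally let the observed sum enter, and at equal 10% drop-out the effect all but cancels. Inverse-probability weighting is not a clear improvement either: without deaths every complete total gets the same weight within an arm, so weighting equals leaving patients out, which was the worse result (0.85 against 0.89) when high users were lost.

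A reader might also infer that unequal deaths produce false-positive tests of hospital days or red-cell units. They do not. A patient who dies has a true total, so if deaths shorten totals in one arm, the totals really differ. Days alive and out of hospital, or ranking death worst, would define other endpoints and would not correct this one.

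**Conclusion.** The point holds as a minor one, confined to secondary endpoints. Two parts rest on the text: the MELD comparison leaves inclusion MELD unused, and the Day 42 and Day 365 windows of the transfusion objective do not reach the endpoint or the analysis. The window mismatch needs no assumption. The precision gain, a variance ratio of about 0.75 to 0.95, rests on assumed correlations of 0.5 to 0.9 and equal SDs at the two visits. The survivor shifts of 0 to 0.6 MELD points rest on assumed deaths, SD and correlations, and serve only to show that neither analysis is free of selection.

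The handling of totals cut short is an optional clarification. The SAP's own drop-out figure gives no material distortion; larger effects need unequal losses that the SAP does not project.

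**What to change.** 1. **MELD.** Analyse Day 180 MELD (or its change from inclusion) by ANCOVA with arm and inclusion MELD. Report by arm the number with a Day 180 value and the deaths before Day 180. State that the result applies to patients alive and measured at Day 180, and that ANCOVA does not remove selection on later deterioration.
2. **Red cells.** In Sections 6.1 and 6.2, specify red-cell units to Day 42 and to Day 365, each compared between arms.
3. **Optional.** Add one sentence on how totals cut short by transplant, consent withdrawal or loss enter the red-cell and hospital-day comparisons. The same sentence can cover glue-arm patients censored at a TIPS placed for another indication (Section 3.1). Show these totals beside mortality and the number cut short, by arm.

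The cost is a few lines of SAP text, best settled before data are compared by arm. Inclusion MELD and the dates of death, transplant and loss are already needed for other analyses. The Day 42 comparison needs transfusions dated so that they can be assigned to the window, which the stated objective already requires. The one statistical downside is the possible larger survivor shift under ANCOVA, which the reporting in item 1 makes visible.
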